4. SCHEDULE OF PROCEDURES

Evaluation Procedure	Screening Visit	Day of Surgery	Discharge	Safety Follow-ups			Study Exit or Early Withdrawal ⁸
				24 h	Every 24 h until discharge	6 weeks	
Informed Consent	X						
Inclusion/Exclusion Criteria	X						
Diagnosis leading to surgery	X						
Planned procedure	X						
Schwab Curve type and coronal curve magnitude (Cobb angle)	X						
Patient age and demography	X						
Medical/Medication Use History	X						
History of previous spine surgery	X						
Height, Weight, Body Mass Index	X						
Number of units of autologous blood donation	X						
CBC: Hb/Hct/WBC/platelet count (post-autologous blood donation)	X						
Coagulation Profile: PT/PTT/INR	X						
Pregnancy Tests ¹	X	X					
Serum Creatinine	X						
Drug / Alcohol /Tobacco Use	X						
Medication Allergies	X						
Physical Examination	X	X					X
Treatment ID		X					
Details of surgical procedure ²		X					
Surgical complications		X					
Surgery time		X					
Volume of cell saver delivered		X					

Blood Collection ³		X	X				
Location of Hemovac drains		X					
Length of drain use			X				
Length of hospital stay			X				
Peri-operative Blood Loss Assessments ⁴		X	X				
Transfusions ⁵		X					
Complications related to transfusions		X	X				
Urine output ⁶		X					
Tranexamic acid related complications ⁷		X	X	X	X	X	X
Functional recovery assessment		X	X	X	X	X	X
Wound Complications		X	X	X	X	X	X

¹ Females must have a negative serum pregnancy test result at screening and a negative urine test prior to surgery.

²Number of vertebrae fused, number of anchors used, and type of anchors used (screws, hooks, or anchors);
Number and type of osteotomies performed

³ Blood for Hb and Hct measurements will be collected pre-surgery, immediately post-surgery, at 24 h and every 24 thereafter until discharge.

⁴ Blood lost during surgery will be collected by subfascial Hemovac drains at the incision site into canisters containing heparinized saline. Volumes collected will be recorded post-surgery and every 24 h thereafter until discharge. Total measured blood loss will be estimated as 3X cell saver; estimates will be taken off of the anesthesia record. The site will provide a person who will collect blood during consult in the OR and record variables and measurements on the data collection sheet throughout the entire surgery. Final blood loss will be measured post removal of the two subfascial hemovac drains placed during the procedure. The total blood loss will be estimated based on the hemoglobin content of the blood prior to surgery (mg/dL), and post-surgery (mg/dL). Blood samples for hemoglobin measurement will be collected prior to start of procedure, at the end of the procedure, at 24 h, and every 24 h thereafter until discharge and removal of the two subfascial drains. Hematocrit analysis will also be conducted on all collected blood samples. The total amounts of fluids infused and amounts of any red blood cell transfusions will be considered, as applicable, in determining the changes in hemoglobin.

⁵ Units of autologous transfusion and allogenic transfusion; Units of fresh frozen plasma and platelets administered; Volume of crystalloids/colloids given.

⁶ Urine output during surgery.

⁷ Symptoms of thromboembolic complications will be followed and recorded. Either radiocontrast venography or pulmonary scintigraphy will be used to confirm deep vein thrombosis or pulmonary emboli. Any observed seizures during the hospital stay will also be recorded and reported.

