6.3. Potential Risks and Benefits

6.3.1. Known Potential Risks²

Visual abnormalities, often poorly characterized, represent the most frequently reported postmarketing adverse reaction in Sweden. No retinal changes have been reported or noted in eye examinations in patients treated with tranexamic acid for weeks to months in clinical trials.

Convulsions have been reported in association with tranexamic acid treatment, particularly in patients receiving tranexamic acid during

cardiovascular surgery and in patients inadvertently given tranexamic acid into the neuraxial system.

Ureteral obstruction due to clot formation in patients with upper urinary tract bleeding has been reported in patients treated with tranexamic acid.

Gastrointestinal disturbances including nausea, vomiting, and diarrhea may occur but disappear when the dosage is reduced. Allergic dermatitis, giddiness and hypotension have been reported occasionally. Hypotension has been observed when intravenous injection is too rapid. To avoid this response, the solution should be not be injected more rapidly than 100 mg/min.

Thromboembolic events such as deep vein thromboses (DVTs) and pulmonary embolism (PE) are associated with tranexamic acid use.

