8.2.2. Secondary Endpoints

The Secondary endpoints include assessment of:

1. Total Measured Blood Loss (measured intra-operatively and for up to 24 hours post-operatively and every 24 hours up to discharge when the two subfascial drains are removed). Total Measured Blood Loss will be estimated as 3 times cell saver.
2. Number of patients with symptomatic anemia (such as tachycardia, hypotension, presyncope) of <8.0 g/dL hemoglobin, or any hemoglobin <7.0 g/dL, precipitated transfusion. *[Alternatively, allogenic blood transfusion will be considered for hemoglobin <9 g/dL intraoperatively or <8 g/dL post-operatively]*
3. Number of patients with adverse events related to tranexamic acid such as confirmed deep vein thrombosis (DVT), pulmonary embolism (PE), or seizures.
4. Other outcomes will include functional recovery, duration of hospital stay, and wound complications (infections, hematomas, and other complications related with surgery).

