10.7.4. Adverse Event Reporting

Any AE (clinical sign, symptom, or disease) temporally associated with the use of this investigational product, whether or not considered related to the investigational product, should be documented on the source document. All AEs reported by the subject or observed by the Principal Investigator will be individually listed. The signs and symptoms, time of onset (24-hour clock), duration, action taken and follow-up procedures will be reported.

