11.3. Populations for Analysis

Up to approximately 150 patients will be enrolled.

The primary analysis population will be a modified Intent to Treat (mITT) population consisting of all subjects receiving an injection of TXA or Placebo.

The secondary analysis population will be a Per Protocol (PP) population consisting of all subjects without major protocol violations (to be

determined by a blinded committee prior to breaking the double-blind code).

The safety population will consist of all subjects receiving an injection of TXA or placebo.

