11.4.4. Safety Analysis

Adverse events will be categorized using MedDRA codes. The TXA and placebo groups will be compared using Fisher exact tests of the number of patients with each category of adverse events. The total number of reported adverse events will also be presented.

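### Footnote 7 names only two tests as confirming DVT or PE, so endpoint 3, which counts confirmed events, may miss events shown by other imaging

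*Combined protocol and SAP*

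**What the plan says.** Section 8.2.2 defines the third secondary endpoint as: "Number of patients with adverse events related to tranexamic acid such as confirmed deep vein thrombosis (DVT), pulmonary embolism (PE), or seizures". The same definition stands in the synopsis objectives, the synopsis endpoints and Section 10.5. None of these places defines what makes an event confirmed.

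Footnote 7 to the Schedule of Procedures (Section 4) is the only place that does so. It begins with surveillance by symptoms, "Symptoms of thromboembolic complications will be followed and recorded", and then states the confirming tests: "Either radiocontrast venography or pulmonary scintigraphy will be used to confirm deep vein thrombosis or pulmonary emboli". It closes on seizures: "Any observed seizures during the hospital stay will also be recorded and reported". The schedule row that the footnote annotates is marked through the 6-week visit. Section 10.3.4 also follows seizures, DVTs and PEs daily in hospital and again at 6 weeks.

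Section 6.3.1 lists thromboembolism among the known risks: "Thromboembolic events such as deep vein thromboses (DVTs) and pulmonary embolism (PE) are associated with tranexamic acid use".

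The adverse event route is separate. Section 10.7.4 provides that "All AEs reported by the subject or observed by the Principal Investigator will be individually listed", whether or not the event is thought related to the product. Section 11.4.4 gives the planned comparison: "The TXA and placebo groups will be compared using Fisher exact tests of the number of patients with each category of adverse events". Section 11.3 sets the population: "The safety population will consist of all subjects receiving an injection of TXA or placebo".

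**The concern.** Footnote 7 is phrased as a rule. It names two methods, with no equivalent or other-imaging clause, and no other section says how to classify an event shown by a different method. A patient may have an objectively imaged DVT or PE and still not meet the stated basis for confirmation unless one of the two named tests is also done. For an event diagnosed at an outside hospital after discharge, the trial does not control which test was used.

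Endpoint 3 is a prespecified endpoint in a study meant to support registration, and it covers a risk the protocol itself names. If real events can drop out because of the imaging method, or if the eight sites each settle the question for themselves, the count is hard to interpret. A low count could then be read as reassurance it does not provide.

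**Working it through.** The plan states no DVT or PE rate, no split of diagnoses by imaging method and no power for endpoint 3, so there is no figure to reproduce. The check is first a comparison of sections, then an illustration on stated assumptions.

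**Step 1: what each route requires.**

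| Route | Imaging confirmation required? | Relatedness required? | Planned test |
|---|---|---|---|
| Endpoint 3 (8.2.2, read with footnote 7) | Yes for DVT; naturally read as also for PE; two methods named | Yes | None specified |
| Listing of adverse events (10.7.4) | No | No | Listing |
| Safety comparison (11.4.4) | No | No | Fisher exact, by MedDRA category |

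Among outcomes normally handled as adverse events, Section 11.4.3 names only symptomatic anemia for analysis. No test restricted to confirmed events is planned. Any loss therefore falls on the endpoint 3 count.

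**Step 2: how a loss would act.** Let s be the share of true events that count as confirmed, taken as equal in the two arms because the trial is double-blind. The expected count in an arm is N × p × s, where p is the true risk.

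- Risk ratio: (pT × s) / (pC × s) = pT / pC, unchanged.
- Risk difference: s × (pT − pC), which shrinks in proportion to s.

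**Step 3: illustration.** From the documents: 100 tranexamic acid and 50 placebo patients (Section 5), and two-sided alpha of 0.05 (Section 11.4.1). The event risks and s are assumptions. Power is exact, found by summing binomial probabilities over all outcomes with Fisher p ≤ 0.05.

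| Assumed risk, active vs placebo | s | Expected counts | Risk difference | Risk ratio | Fisher power |
|---|---|---|---|---|---|
| 5% vs 2% | 1 | 5 vs 1 | 3.0 points | 2.5 | 2.5% |
| 5% vs 2% | 0.5 | 2.5 vs 0.5 | 1.5 points | 2.5 | 0.2% |
| 10% vs 2% | 1 | 10 vs 1 | 8.0 points | 5 | 33% |
| 10% vs 2% | 0.75 | 7.5 vs 0.75 | 6.0 points | 5 | 17% |
| 10% vs 2% | 0.5 | 5 vs 0.5 | 4.0 points | 5 | 4% |
| 15% vs 2% | 1 | 15 vs 1 | 13.0 points | 7.5 | 73% |
| 15% vs 2% | 0.5 | 7.5 vs 0.5 | 6.5 points | 7.5 | 21% |

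Example: 100 × 0.10 × 0.5 = 5 and 50 × 0.02 × 0.5 = 0.5. At s = 1 nothing is lost; at s = 0 no event counts in either arm. The documents do not place s within that range. The power column describes a hypothetical test of confirmed events only. The Section 11.4.4 comparison corresponds to s = 1, provided that events diagnosed by other methods are coded as DVT or PE and not merely as symptoms.

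**Step 4: seizures.** Footnote 7 refers to seizures during the hospital stay. The schedule row it annotates and Section 10.3.4 run to 6 weeks. The two windows differ for a named component of endpoint 3.

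**The case against.** The strongest reply is that the footnote neither says that only these two methods count nor discards events shown another way. It can be read as an instruction to perform a confirming test. If sites follow it, in-trial events receive that test and none is lost. This stands for events worked up at the trial sites. It does not cover events diagnosed elsewhere after discharge, and it leaves the classification unwritten where another method was used.

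A reader might infer that the main safety comparison is undercounted. The documents do not support that. No section calls endpoint 3 the key safety comparison, and the Fisher tests in Section 11.4.4 use coded adverse events with no confirmation or relatedness filter. The one condition is the coding noted above, which the plan does not spell out.

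A reader might also infer that the words limiting endpoint 3 to related events would exclude most post-operative thromboses. Section 10.7.2 does not bear this out. Its Possible grade accepts a reasonable time sequence or a known response pattern even where other causes could explain the event. The protocol does not say which grades count as related.

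On seizures, the footnote's sentence adds to the general adverse event capture and does not cancel it. The conflict is real but minor.

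Finally, small numbers limit inference whatever the imaging rule: at an assumed 5% vs 2%, Fisher power is 2.5% even with complete counting.

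**Conclusion.** The point holds as a defect in the definition of endpoint 3. Read literally, the plan may leave out an objectively imaged DVT or PE because of the method used, most plausibly when it was diagnosed outside the trial sites before the 6-week visit, and the endpoint 3 count may then be too low. The Section 11.4.4 comparison is not shown to be affected.

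No size can be given. The share of events diagnosed by other methods is not in the documents and could be 0% to 100%, so the loss could be none or all of them. If it is equal in both arms, the counts, the risk difference and the power of any confirmed-only test fall, while the risk ratio does not change. Neither bias in the risk ratio nor a false conclusion of safety from the planned tests follows from the text. This is worth correcting because it is cheap and concerns a named risk; it does not undermine the trial.

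**What to change.** 1. In footnote 7 and wherever endpoint 3 is defined, state that for counting purposes a DVT or PE is confirmed when documented by any objective imaging or at autopsy, including reports from outside hospitals. This is a counting rule and should not direct which test clinicians order.
2. Record modality and date of diagnosis on the CRF.
3. Reconcile the in-hospital seizure window in footnote 7 with the 6-week follow-up in the schedule and Section 10.3.4.
4. Report endpoint 3 events by arm for all events regardless of attribution, with the related subset beside them and the grades that make up that subset stated.

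The cost is wording in a few places, a CRF entry for modality and date, and a table. No additional test is needed. The small downside is that several modalities then contribute to one endpoint; a tabulation by modality shows this openly. The definition should be fixed before unblinding.

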5. SCHEMATIC OF STUDY DESIGN

CP-006-2017 – Efficacy and safety of tranexamic acid in spinal fusion surgery

- ❖ Study Cohort - > Adult patients over age 18 electively undergoing complex spinal fusion surgery (T2 to pelvis/Sacrum, greater than 4 FSU's (5 vertebral segments or more)).
- ❖ Arm 1 - > Subjects receiving study drug (treat) (n = 100).
- ❖ Arm 2 - > Subjects receiving placebo (control) (n = 50).
- ❖ Sample size - > 150 study subjects; randomized 2:1 Treat / Control
- ❖ Intervention: Arm1 – Surgery plus study drug
Arm 2 – Surgery with placebo

6. BACKGROUND INFORMATION

6.1. Background and Literature

Tranexamic acid is a synthetic derivative of the amino acid lysine that inhibits fibrinolysis by competitively inhibiting plasminogen activation, and to a lesser extent, noncompetitively inhibiting plasmin. Tranexamic acid binds to lysine binding sites on plasminogen and plasmin thereby blocking the action of lysine and preventing fibrin clot breakdown. It is used to treat or prevent excessive blood loss during surgery and in various coagulopathies. Following intravenous administration, tranexamic acid has a half-life for the terminal elimination phase of about 2 hours. Urinary excretion is the main route of elimination via glomerular filtration. Overall renal clearance is equal to plasma clearance of 110-116 mL/min, and more than 95% of the dose is excreted in the urine as unchanged drug.

Recently, the intravenous administration of a 1-gram loading dose and 1-gram 8-hour continuous infusion of tranexamic acid has been shown to reduce all-cause mortality and mortality due to blood loss from serious hemorrhagic trauma injuries¹. The CRASH-2 trial showed that administration of tranexamic acid to adult trauma patients with, or at risk of, significant hemorrhage within 8 hours of injury significantly reduced all-cause mortality with no apparent increase in vascular occlusive events. As a consequence of this trial, tranexamic acid has been incorporated into trauma treatment protocols worldwide. Tranexamic acid was added to the WHO list of essential medicines following the CRASH-2 study. In addition, numerous studies report the benefits and safety of tranexamic acid in cardiac, gynecological, and orthopedic surgeries. Albeit off-label, tranexamic acid is part of the standard of care protocols of several orthopedic surgery centers for total knee-arthroplasty and hip replacement in the United States.

In the United States, FDA approved indications for tranexamic acid, are limited. It is indicated for treatment of patients with hemophilia to reduce or prevent hemorrhage and reduce the need for replacement therapy during and following tooth extraction, and for the treatment of menorrhagia in women.

The current dosage regimen for intravenous tranexamic acid is to administer 10 mg/kg of CYKLOKAPRON intravenously immediately before tooth extraction in patients with hemophilia. Following tooth extraction, intravenous therapy, at a dose of 10 mg/kg, 3 to 4 times daily may be used for 2 to 8 days.²

Exela Pharma Sciences has developed Tranexamic Acid Premixed Injection 10 mg/mL in 0.7% sodium chloride (1 gram tranexamic acid/100 mL). The pH of the product is 6.5 to 8.0 and the osmolality is approximately 285 mOsmol/kg. Exela is seeking FDA approval and registration for indications related to the reduction of perioperative blood loss.

6.2. Rationale

As stated earlier, the CRASH-2 study established the safety and efficacy of tranexamic acid use in reducing blood loss in trauma situations and numerous reported studies support the safety and efficacy of tranexamic acid use for reduction of blood loss (or transfusions) in cardiac, gynecologic, and orthopedic surgeries. In addition, several surgical centers within the United States use tranexamic acid as part of their standard protocol during total knee-arthroplasty and hip replacement surgeries. However, this use of tranexamic acid is currently off-label. Exela intends to obtain approval for its tranexamic acid product for the indication of “reduction of perioperative blood loss”.

Several literature reported studies have shown tranexamic acid to be effective in reducing perioperative blood loss in spinal fusion surgeries.³⁻⁹ However, most of these studies showing efficacy of tranexamic acid in spinal surgery were conducted outside the United States and used varying dosing regimens. For example, one study reported by Shapiro F, et.al., conducted at Childrens Hospital Boston and Harvard Medical School used high doses of tranexamic acid (100 mg/kg administered over 15 min, followed by a 10 mg/kg infusion throughout the surgery).³ These authors reported that blood loss was reduced by 42% in the tranexamic acid treated group. A Canadian study by Wong J, et.al., reported a 25-30% reduction in blood loss using a 10 mg/kg initial dose

followed by a maintenance infusion of 1 mg/kg/h until skin closure.⁴ Another study by Grant JA, et al., compared a tranexamic acid bolus dose of 10 mg/kg followed by a 1 mg/kg/h infusion with a bolus dose of 20 mg/kg followed by a 10 mg/kg/h infusion in patients with idiopathic scoliosis and reported a 50% reduction in blood loss following the high dose.⁵ Verma K et al. reported a study plan to compare a low dose tranexamic acid regimen to a high dose tranexamic acid regimen for use in spinal fusion surgeries.⁶ A meta-analysis that consolidated the findings of 11 randomized controlled trials which investigated the use of TXA on surgical bleeding in spine surgery concluded that surgical bleeding and transfusion requirements are reduced using TXA and that there is no apparent association with increased incidence of pulmonary embolism, DVT, or MI.⁷

In summary, substantial support for the use of intravenously infused tranexamic acid in the field of spinal surgery exists.^{8,9} Exela aims to use the currently approved dosing regimen of “10 mg/kg initial dose followed by 3-4 doses of 10 mg/kg per day” as the basis for the dosing regimen to be used in this study. The maximum dose as per the currently approved dosing regimen is 50 mg/kg (10 mg/kg initial dose + 4 doses of 10 mg/kg per day). The maximum dose to be administered is maintained as 50 mg/kg per day in the current protocol. However, the dosing regimen is modified as “30 mg/kg over 1-hour as an initial dose prior to surgery and an infusion dose of 3 mg/kg/h throughout the surgery up to a maximum of 50 mg/kg”.

6.3. Potential Risks and Benefits

6.3.1. Known Potential Risks²

Visual abnormalities, often poorly characterized, represent the most frequently reported postmarketing adverse reaction in Sweden. No retinal changes have been reported or noted in eye examinations in patients treated with tranexamic acid for weeks to months in clinical trials.

Convulsions have been reported in association with tranexamic acid treatment, particularly in patients receiving tranexamic acid during

cardiovascular surgery and in patients inadvertently given tranexamic acid into the neuraxial system.

Ureteral obstruction due to clot formation in patients with upper urinary tract bleeding has been reported in patients treated with tranexamic acid.

Gastrointestinal disturbances including nausea, vomiting, and diarrhea may occur but disappear when the dosage is reduced. Allergic dermatitis, giddiness and hypotension have been reported occasionally. Hypotension has been observed when intravenous injection is too rapid. To avoid this response, the solution should be not be injected more rapidly than 100 mg/min.

Thromboembolic events such as deep vein thromboses (DVTs) and pulmonary embolism (PE) are associated with tranexamic acid use.

6.3.2. Known Potential Benefits

Several studies as discussed in Section 6.2 show that tranexamic acid can reduce perioperative blood loss and accidental trauma.

7. TRIAL OBJECTIVES AND PURPOSE

The purpose of this study is to assess the efficacy and safety of tranexamic acid using a dosage regimen similar to that used in the currently approved indication (intravenous therapy of patients with hemophilia during and following tooth extraction) for the reduction of blood loss and minimizing transfusion rates in patients undergoing spinal fusion surgery. This study will be used to support registration and labeling of Exela's Tranexamic Acid products for use in the United States for this indication.

